Surgical cases requiring sedation by an anesthesia provider, also known as monitored anesthesia care (MAC), are a popular choice for outpatient surgical procedures with benefits of “less physiologic disturbance and a more rapid recovery than general anesthesia” (Das 2015). However, MAC cases still come with risk: per the American Society of Anesthesiologists closed claim database, “the most common malpractice claim is inadequate oxygenation/ventilation, with more than 80% of claims of this nature resulting in brain damage or death” (McMurray 2020). Since 1908, anesthesia providers have been utilizing interventional airway devices that manipulate the soft tissues of the nasopharynx, oropharynx, and hypopharynx to relieve obstruction to support patient ventilation and oxygenation; however, there are few studies that directly compare the efficacy & side effect profiles between these devices (Matioc 2019). Additionally, a recent survey indicates that many anesthesia providers desire an alternative airway intervention device than the current ones most commonly used in current practice (McMurray 2020). We will examine the possibility of using at-home, over-the-counter anti-snoring devices as an intraoperative airway device.

STUDY ENDPOINTS:

PRIMARY ENDPOINT: Combined total number of airway interventions during an anesthetic sedation case – including head tilt/rotation, mandible thrust, chin lift, shoulder lift, neck extension or flexion, tongue pull.

SECONDARY ENDPOINTS:

- Satisfaction of Anesthetist via survey
- Maximum/minimum end-tidal CO₂
- # of times SpO₂ value < 92%
- % of time during the case SpO₂ < 92%
- maximum/minimum SpO₂ value
- EKG analysis that were not recorded as “Normal Sinus rhythm”:
- Heart rate maximum & minimum
- maximum/minimum Systolic, diastolic, and mean blood pressure
- Total dose and type of hypnotic & narcotic given
- Case type
- Case duration
- Baseline characteristics (Age, Gender, BMI)

- Time spent in Phase 2 PACU Recovery
- Adverse events (i.e. regurgitation and aspiration, bronchospasm, cough, case converted to GA)

STUDY INTERVENTION(S) / INVESTIGATIONAL AGENT(S):

We will use anti-snoring appliance devices (specifically the FDA approved Zyppah) to attempt to relieve tissue obstructions that cause snoring during sleep. The application of the devices to the body is less invasive than other common intraoperative rescue airway devices (e.g. nasal trumpets and oral airways) which are not designed to be patient specific.

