We will be purchasing the device from the manufacturer's website. We will be purchasing the devices via funds awarded by the James E. Eckenhoff Residents' Research Award.

The device will be stored in the PI's key-locked office, until it is given to a research team member to be given to a subject after recruitment and prior to their procedure. Research personnel will bring the appliance to the preoperative holding area & will help mold it for the patient, and will insert it prior to transport to the operating suite. The device will remain in place until the completion of procedure, unless the anesthesia provider in the room feels it needs to be removed for any reason. The patient or anesthesia personnel can remove the device at their leisure after completion of the procedure.

PROCEDURES INVOLVED:

The study participants will be recruited into two groups: patients wearing an anti-snoring appliance device during an anesthetic sedation procedure; and those who do not wear an anti-snoring device. To ensure anesthetic providers have easy access to the patient's airway for standard of care manipulation (if needed), the patients eligible for this study would be those who are undergoing procedures below the umbilicus (e.g. gynecological, urological, orthopedic, etc.) in addition to having a STOP-BANG score of 2 or greater. This will ensure patient safety and provide a wide demographic of potential subjects to increase the generalizability of the study.

For both patient groups, the study procedure is the same. Eligible patients will be identified by chart review of various elements of the electronic medical record, as follows:

Patients will be identified and be seen by the study team in the pre-operative clinic on 17th floor Lavin and in the holding area to interview individuals who are to undergo eligible anesthetic sedation procedures as above. If the patient agrees to participate in the study, they will be randomized at that time to one of the two groups (anti-snoring appliance device to be used for procedure or not).

The groups in the prospective, randomized, controlled trial in patients undergoing anesthetic sedation procedures will be as follows:

Group #1: Anti-snoring appliance (Zyppah) that will be utilized during their procedure
Group #2: Control group, that will not utilize anti-snoring appliance

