Individual subjects and anesthetic providers will participate in the study for the duration of their procedure requiring anesthetic sedation. It will take approximately 3 months to enroll participants and approximately 3 months to perform data analysis.

INCLUSION AND EXCLUSION CRITERIA

Inclusion criteria

Adult patients (age 18-89 years old)

Undergoing procedures below the umbilicus requiring anesthetic sedation without an invasive airway

STOP-BANG score of 2 or greater.

English or Spanish language speaking

Exclusion criteria

Patients requiring general anesthesia.

Sleep apnea

Serious breathing or respiratory disorders such as COPD, asthma, emphysema

Poor dental health including severe gum disease, loose teeth, abscess, mouth sores, bleeding gums

Dental implant place within last 3 months

TMJ disorder

Mouth or jaw pain

Full dentures

Wear braces

Sleep with CPAP or other devices

Other special populations (individuals who are not yet adults, prisoners, vulnerable populations, pregnant) will also be excluded.

VULNERABLE POPULATIONS:

Will not be a part of study.

PARTICIPANT POPULATION(S)

Accrual Number:	Category/Group: (Adults/Children Special/Vulnerable Populations)	Consented: Maximum Number to be Consented or Reviewed/Collected/Screened	Enrolled: Number to Complete the Study or Needed to Address the Research Question
Local	Adults	28	28
Study-wide		28	24
Total:		28	24

RECRUITMENT METHODS

Patients undergoing an eligible procedure requiring anesthetic sedation will be identified by the anesthesiology team by chart review and the schedule in the pre-operative clinic on the 17th floor Lavin pavilion prior to their procedure. They may also be approached by the research team the morning of their procedure for possible enrollment into the study. If the potential subject is interested in the study a study team member will ask for the subject's email address to send an Econsent using REDCap for their review.

The source of participants will be NMH pavilions (Galter, Feinberg, Lavin) in addition to Prentice Women's Hospital.

COMPENSATION FOR PARTICIPATION IN RESEARCH ACTIVITIES

There will be no compensation for participation; however, patients who are randomized into one of the anti-snoring device groups will be allowed to keep the device, if they wish.

WITHDRAWAL OF PARTICIPANTS

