Patients can withdraw from the study at any time and their data will be deleted, and in no way will this impact their care since the study explicitly does not affect the standard of care. The study team will notify the PI by secure NM or NU email if a subject withdraws from the study.

RISKS TO PARTICIPANTS

No significant risk to the patient exists with the utilization of an anti-snoring device. The devices are non-invasive and can be easily removed by the patient or anesthesia provider, if needed. There is the potential for damage to loose teeth, gums or tongue since this is a moldable mouth guard. There is the potential for loss of confidentiality even with strict measures in place to prevent occurrence.

POTENTIAL BENEFITS TO PARTICIPANTS

If functional, the participants may benefit from utilization of an anti-snoring device by reducing snoring and airway obstruction; which would lead to improved sleep and less fatigue. It may also prevent the use of more invasive rescue airway devices that can cause patient discomfort including damage to the lips, teeth, gums, tongue, naso- and oropharynx.

DATA MANAGEMENT AND CONFIDENTIALITY

Data Statistics:

Preparation: In previous studies looking at patient satisfaction for snoring relief, 570 participants were analyzed with one of the anti-snoring devices resulting in a statistically significant benefit. However, there are currently no large published studies that analyze the use of an anti-snoring devices in the setting of MAC anesthesia. Additionally, there are no large studies comparing the efficacy of traditional invasive airway rescue devices (e.g. oral/nasal airways).

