We utilized a study by Qiansong Xiao et al titled “Comparison of Nasopharyngeal Airway Device and Nasal Oxygen Tube in Obese Patients Undergoing Intravenous Anesthesia for Gastroscopy: A Prospective and Randomized Study”, which compared the oxygen saturation levels in patients who did or did not have an invasive nasopharyngeal airway at the beginning of the anesthetic sedation procedure, to perform our power analysis. 260 patients were included and randomized; with 3 patients excluded due to failure of the nasopharyngeal airway. Based on the differences in “change in SpO₂” and “raising the mandible” between their test and control groups, and power analysis was completed with an alpha value of 0.05 and power value of 80%. The n per group that was calculated to provide the appropriate power to identify a statistical difference was 12 patients per study group. To compensate for patients in our study being less obese we increased the number per group to 14 subjects. We plan to approach 28 subjects and randomize 28 patients to 2 groups, allowing for patients who may not end up getting their procedure or instances where data collection is incomplete or absent.

Statistical analysis: Data will be compared between all groups using paired t-test with p< 0.05 required to reject the null hypothesis.

Data Security:

All collected data will be stored in REDcap using NM password protected computers for data entry. Data in REDcap is backed up nightly using NM servers which are only accessible to the NM IT administrator. Paper documents generated during the study will be stored in Arkes Pavilion 10th floor Department of Anesthesiology locked research cabinet. Data both paper and electronic will be destroyed 5 years after the completion of the study using current department policy and approved vendors.

PROVISIONS TO MONITOR THE DATA TO ENSURE THE SAFETY OF PARTICIPANTS N/A

PROVISIONS TO PROTECT THE PRIVACY INTERESTS OF PARTICIPANTS

Patients in this study undergoing a procedure under anesthetic sedation can be stressful. If a subject does not feel comfortable with participating, they will have the option to opt out at any time and it will not impact their care if they choose to do so.

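### Safety monitoring is entered as not applicable: the protocol states no review, report or pause step after a serious event, and its adverse-event list omits the oral injury it names as a device risk

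*Combined protocol and SAP*

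**What the plan says.** The safety-monitoring entry is "PROVISIONS TO MONITOR THE DATA TO ENSURE THE SAFETY OF PARTICIPANTS N/A", and the Study Summary marks that there is no DSMB. Risks to Participants opens with "No significant risk to the patient exists with the utilization of an anti-snoring device" and then adds "There is the potential for damage to loose teeth, gums or tongue since this is a moldable mouth guard". The secondary endpoints include "Adverse events (i.e. regurgitation and aspiration, bronchospasm, cough, case converted to GA".

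The protocol does contain safeguards:

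- **Eligibility** excludes "Poor dental health including severe gum disease, loose teeth, abscess, mouth sores, bleeding gums" and "Serious breathing or respiratory disorders such as COPD, asthma, emphysema", as well as recent implants, jaw disorders, mouth or jaw pain, full dentures and braces.
- **Airway access** is protected by limiting the study to procedures below the umbilicus.
- **Removal:** the device stays in until the procedure ends "unless the anesthesia provider in the room feels it needs to be removed for any reason".
- **Supply:** devices are kept locked in the principal investigator's office until issued (Study Intervention).
- **Observation:** research staff watch the case to collect the outcome measures and review the anesthetic record afterwards (Procedures Involved). They also meet the provider for about five minutes after the case (Provisions to Protect the Privacy Interests).
- **Charting:** charted adverse events and provider free text are extracted (Data and Specimen Banking).

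The only participant event that the team must notify to the principal investigator is withdrawal (Withdrawal of Participants).

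**The concern.** The not-applicable entry appears to rest on the statement that there is no significant risk. Yet the trial takes a home-use, over-the-counter device into the operating room as an airway aid under sedation, and Data Statistics says that no large published study has examined such devices in that setting. The protocol itself counts aspiration, bronchospasm and conversion to general anesthesia as adverse events worth recording.

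Two things are at stake. First, if the protocol is followed as written, the next patient can receive the device after a possibly device-related aspiration without any review that the protocol calls for. Second, the trial could end with no usable account of the oral harm it named. A report of no oral injuries might mean only that nobody was asked to look.

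**Working it through.** The plan gives no figure to reproduce here, so the check is mainly a reading of the text.

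**1. Is there a duty to act after a serious event?**

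| Step | What the protocol states |
|---|---|
| Notice to the principal investigator | For withdrawal only |
| Judgement of seriousness or device-relatedness | Nobody named |
| Report to the IRB or others | No route or deadline |
| Pause of device use or randomization | No rule |
| Action for the patient in the room | Provider may remove the device |

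The last row protects the current patient, not the next one. Locked storage would let the principal investigator stop supply, but no rule says when. Record review follows each case, with no stated deadline and no consequence attached.

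**2. Is the named oral harm covered?**

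| Harm named under Risks | Removed by eligibility? | On the adverse-event list? |
|---|---|---|
| Loose teeth | Yes, excluded | No |
| Gums | In part: existing gum disease and bleeding are excluded, new injury is not | No |
| Tongue | No | No |

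The list is introduced by *i.e.*, which closes it. Observers are there to collect the outcome measures, and oral injury is not one of them. The remaining recorded route is charting and free text, which depends on a provider choosing to write the injury down. The protocol does not say what the five-minute meeting covers. The only post-case questions it describes, a satisfaction survey, go to providers in the device group alone.

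**3. What can be sized?**

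- Device patients: 14 (Data Statistics).
- One device patient treated without the device because of a pause: 1/14 = 7.1% of the arm.
- If every device patient were checked and none had an injury, the one-sided 95% upper limit for the true rate would be 1 − 0.05^(1/14) = 0.193, or 19.3%. With 12 patients it would be 1 − 0.05^(1/12) = 0.221, or 22.1%.

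So this trial cannot establish safety by counting events, even with full collection. The gain from the fix is that any event is recorded and acted on case by case.

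**The case against.** The strongest reply is that this is a documentation gap in a well-watched 28-patient study. Staff observe the cases and review the records. The team includes two resident physicians and a research assistant on the anesthesia care team, and the provider can take the device out at any time. A serious event would be hard to miss, and IRB policy would probably require a report. Eligibility removes the patients most prone to dental injury, and chart extraction is not limited by type of event. The abbreviation before the adverse-event list may be a slip for *e.g.*

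Much of this stands. A reader might infer that nobody is obliged to assess or report anything, but the documents do not support that. IRB policy is not in the document and the consent pages were removed, so the most that can be said is that the protocol does not state a duty. A reader might also infer that safety data are absent, and they are not.

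Two things are left unanswered. Gum and tongue injury remain possible after the exclusions, and even if the list is read as examples, nobody is told to look for them. A general IRB reporting duty would not by itself add oral injury to the collected data or say when device use stops.

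**Conclusion.** The point holds as a modest, cheap improvement to safety conduct. The protocol enters safety monitoring as not applicable and states no investigator-level step to review, report or pause. It also leaves out of its adverse-event list the physical harm that it attributes to the device. The conclusion assumes only that the document as available is the operative text, and it allows that duties may exist elsewhere.

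No amount of harm is claimed. With "It will take approximately 3 months to enroll participants" in the protocol, a reader might want to work out how likely another device case is before a review. That figure would be conditional on an event having occurred and on a review delay, and the documents give neither an event rate nor a delay. It would not measure harm to patients.

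A reader might also infer that a DSMB is needed. For 28 patients at what appears to be one site, with a device described as FDA approved, its absence is not a fault.

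**What to change.** 1. **Adverse-event list.** Add injury to teeth, gums or tongue to the secondary endpoints. Have the research personnel already present check for it and record it in both groups at the end of the case, after device removal in the device group.
2. **Safety-monitoring section.** Replace the not-applicable entry with:
   - same-day notice to the principal investigator of any aspiration, bronchospasm, conversion to general anesthesia or oral injury, in either group;
   - the principal investigator's judgement of seriousness and device-relatedness;
   - reporting to the IRB under its policy;
   - after a serious, possibly device-related event, a pause of device use and of randomization until the principal investigator documents a decision to resume or stop.

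The notice should cover both groups because providers are unblinded and adverse events are compared between groups. Closer scrutiny of the device group alone would invite unequal ascertainment. Same-day notice by itself does not protect the next patient; the pause does.

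**Cost.** One paragraph, one list item and a brief look in the mouth. The protocol describes staff contact with participants only before the procedure, so the check adds a short contact afterwards, and Study Timelines should allow for it. A serious event may bring a short enrolment pause. Taking three months as 13 weeks (assumed), 14/13 is about 1.1 device patients per week, so a one-week pause would on average meet about one. A patient already randomized to the device may then have the procedure without it (7.1% of the arm for one patient) and should be analysed as randomized. With no serious event, nothing is delayed.
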